12.7 Interim analyses

[REDACTED]

[REDACTED]

[REDACTED]

Further details will be provided in DMC Charter and Statistical Analysis Plan.

[REDACTED]

[REDACTED]

[REDACTED]

At the End of Study, a final analysis of all data collected up to last study visit will be performed when all subjects have completed the last study visit.

12.8 Sample size calculation

Sample size requirements for this study are primarily driven by HiSCR at Week 16 endpoints. A 5% two-sided type-I-error rate will be used to control for type I error. Two secukinumab doses will be tested versus placebo with respect to the primary endpoint (HiSCR at Week 16). The type-I-error will be split to 4% and 1% two-sided for secukinumab 300 mg q2w vs. placebo and secukinumab 300 mg q4w vs. placebo, respectively. Sample sizes will be based on this type-I-error assumption.

A total of 471 patients was originally planned to be randomized to study drug in a 1:1:0.5:0.5 ratio. A second study of identical design with the same sample size will be conducted in parallel. Both studies are independently powered to address the primary endpoint (HiSCR) and secondary endpoint on flare. The secondary endpoint on pain will be analyzed in the combined populations of both trials, provided the primary null-hypothesis can be rejected in both studies. All sample size calculations were done in nQuery Advisor 7.0.

As discussed in [Section 5](#), to account for the disruptive impact of the COVID-19 pandemic on the conduct of the study since the release of protocol amendment 01, the number of randomized patients was increased to approximately 541 (15% increase from the original population of 471 patients).

12.8.1 Primary endpoint(s)

HiSCR: Based on adalimumab phase III placebo-controlled studies (PIONEER I and II, respectively, [Kimball et al 2016](#)), a placebo response rate of 30% is assumed. The original total sample size of 471 patients for this trial is sufficient to achieve 93% power for the demonstration of 20% difference of secukinumab 300 mg q2w over placebo based on the primary endpoint (HiSCR) when assuming a secukinumab response rate to be 50%. In regards to the comparison of secukinumab 300 mg q4w to placebo, we achieve 83% power to show superiority.

12.8.2 Secondary endpoint(s)

The power mentioned for the Secondary endpoints is conditional on the successful rejection of the null hypothesis for the primary endpoint (HiSCR), and the testing procedures are defined in [Section 12.5.1](#).

Percentage change in AN count: based on adalimumab phase III placebo-controlled studies (PIONEER I and II, respectively ([Kimball et al 2016](#))), it is assumed that the difference between secukinumab and placebo is at least 18% in favor of secukinumab when considering the mean percentage change from baseline in AN count at Week 16. Although it is planned to use a repeated measures model for the analysis, an approximate sample size can be based on a simple t-test. The original sample size of 471 patients is sufficient to achieve 92% power in secukinumab 300 mg q2w vs. placebo and 81% power in secukinumab 300 mg q4w vs. placebo when assuming a standard deviation of 46%.

Flare: Based on adalimumab phase III placebo-controlled studies (PIONEER I and II, respectively, [Kimball et al 2016](#)), a placebo rate of 35% is assumed. The original sample size

of 471 patients is sufficient to achieve 98% power for the demonstration of 20% difference of secukinumab 300 mg q2w over placebo based on the second endpoint when assuming secukinumab 300 mg q2w rate to be 15%. Assuming the same rate for secukinumab 300 mg q4w, the sample size would be sufficient to achieve 92% power in a comparison of secukinumab 300 mg q4w vs. placebo.

Pain: Based on adalimumab phase III placebo-controlled studies (PIONEER I and II, respectively, [Kimball et al 2016](#)), a placebo rate of 23% is assumed. Assuming 80% patients are qualified to calculate Pain variable NRS30, the original total sample size of 942 patients across two studies is sufficient to achieve 85% power for the demonstration of 13% difference of secukinumab 300 mg q2w over placebo based on the second endpoint when assuming the rate to be 36%. The original sample size is also sufficient to achieve 70% power to demonstrate superiority of secukinumab 300 mg q4w over placebo based on the same assumptions in regards to the rates of secukinumab and placebo as above.

13 Ethical considerations and administrative procedures

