Testing procedure and type-I-error control in the planned submission includes studies CAIN457M2301 and CAIN457M2302 (both with identical design). Hypotheses can only be tested in the order as indicated by the arrows. The hypothesis H1 of the primary objective (HiSCR at Week 16) for the high dose secukinumab regimen (q2w) versus placebo will be tested at $4\alpha/5$ while the hypothesis H2 of the primary objective (HiSCR at Week 16) for the low dose secukinumab regimen (q4w) versus placebo will be tested at $\alpha/5$ simultaneously. If at least one of H1 and/or H2 are/is rejected then H3 and/or H4 (percentage change from baseline in AN count at Week 16), is tested. If at least one of H3 and/or H4 are/is rejected, then the corresponding alpha will be passed to H5 and/or H6 (flare over 16 weeks) respectively. Once HiSCR, percentage change in AN count and flare hypotheses for a secukinumab regimen are rejected, the respective $4\alpha/5$ for the high dose and $\alpha/5$ for the low dose can be passed on to the other regimen's hypotheses, if they are not already rejected at the initial significance level (i.e., $\alpha/5$ for the low dose and $4\alpha/5$ for the high dose). If both studies independently reject the primary null-hypothesis on the same secukinumab regimen (H1 and H'1, or H2 and H'2), then the corresponding secukinumab regimen's pain hypothesis (H7 or H8) can be tested. Additionally,

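### Flare powers of 98%/92% are stated as conditional on HiSCR alone, yet they exceed the 92%/81% given for the AN-count test that must be rejected first

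*Protocol*

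**What the plan says.** Protocol 12.8.2 opens with one condition for all secondary endpoints: "The power mentioned for the Secondary endpoints is conditional on the successful rejection of the null hypothesis for the primary endpoint (HiSCR". It refers to 12.5.1 for the testing procedure. For AN count, the original 471 patients are "sufficient to achieve 92% power in secukinumab 300 mg q2w vs. placebo and 81% power in secukinumab 300 mg q4w vs. placebo". For flare, that size "is sufficient to achieve 98% power for the demonstration of 20% difference of secukinumab 300 mg q2w over placebo" and, at the same assumed rate, "the sample size would be sufficient to achieve 92% power in a comparison of secukinumab 300 mg q4w vs. placebo". SAP section 3 repeats the condition and all four figures, and refers to the Week 16 SAP for the procedure.

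Protocol 12.5.1 sets the order: "Hypotheses can only be tested in the order as indicated by the arrows". Within a regimen, HiSCR (H1/H2) comes first, then AN count (H3/H4), then flare. Only when H3 and/or H4 is rejected "then the corresponding alpha will be passed to H5 and/or H6 (flare over 16 weeks) respectively". Alpha moves to the other regimen only at the end of a chain: "Once HiSCR, percentage change in AN count and flare hypotheses for a secukinumab regimen are rejected".

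Two related statements differ between the documents:

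- **Powering.** Protocol 12.8 says "Both studies are independently powered to address the primary endpoint (HiSCR) and secondary endpoint on flare". The matching sentence in SAP section 3 adds AN count.
- **Enlarged size.** SAP section 3 gives it as approximately 541 in its opening text and as 544 under the primary endpoint. Both are described as a 15% increase on 471.

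**The concern.** Rejecting flare in a regimen implies that AN count was rejected in that regimen. Given HiSCR success, the chance of a flare claim can therefore be no larger than the chance of an AN-count claim. The plan puts both under the same condition and states the reverse order for both regimens: 98% above 92%, and 92% above 81%.

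Flare is a confirmatory secondary endpoint. A reader would take 98% as the chance of a q2w flare claim once HiSCR has succeeded, and would read a missed flare result against that figure.

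**Working it through.** **Inputs.** All are from Protocol 12.8 to 12.8.2, with placebo pooled as in 12.1.

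- 471 patients at 1:1:0.5:0.5, so 471/3 = 157 per compared group
- Two-sided alpha 4% (q2w) and 1% (q4w); critical z 2.054 and 2.576
- HiSCR 30% v 50%; AN count difference 18, SD 46; flare 35% v 15%

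**Step 1: reproduce the plan's figures, one endpoint at a time.** For proportions, power = Φ[(d − 1/n − z·s0)/s1], with s0 = √(2p̄(1−p̄)/n), s1 = √((p1q1 + p2q2)/n) and 1/n = 0.00637 as continuity correction.

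- HiSCR: s0 = 0.05529, s1 = 0.05413.
  - q2w: (0.19363 − 2.054 × 0.05529)/0.05413 = 1.479, power 93.0%
  - q4w: (0.19363 − 2.576 × 0.05529)/0.05413 = 0.946, power 82.8%
- Flare: s0 = 0.04887, s1 = 0.04755.
  - q2w: (0.19363 − 2.054 × 0.04887)/0.04755 = 1.961, power 97.5%
  - q4w: (0.19363 − 2.576 × 0.04887)/0.04755 = 1.425, power 92.3%
- AN count (t-test): noncentrality (18/46)√(157/2) = 3.467 on 312 df. Power is 91.9% at 4% and 80.9% at 1%.

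The stated figures are 93/83, 98/92 and 92/81, so all six reproduce as single-test powers. The plan does not mention a continuity correction. Without it, q4w flare would be 94.0%, and the corrected version fits throughout.

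**Step 2: the bound.** In either regimen, and with or without alpha passed from the other, {flare rejected} is contained in {AN count rejected}. So P(flare | HiSCR) ≤ P(AN count | HiSCR). The stated 98 > 92 and 92 > 81 both break this, at any correlation.

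**Step 3: power of the full procedure.** Six normal statistics were simulated with 1,000,000 draws. Each regimen's chain HiSCR → AN count → flare ran at 4% or 1%. A fully rejected chain passed its alpha, and the other chain was retested at 5%. The documents give no correlations. Those between endpoints were set at 0 to 0.8, and that between regimens at 0.5. Results at 157 per arm:

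| Endpoint correlation | Flare given HiSCR, q2w | Flare given HiSCR, q4w | Flare, unconditional, q2w | Flare, unconditional, q4w |
|---|---|---|---|---|
| 0 | 90.5% | 88.3% | 84.7% | 80.6% |
| 0.3 | 91.9% | 90.3% | 86.0% | 82.4% |
| 0.5 | 93.1% | 92.1% | 87.1% | 84.0% |
| 0.8 | 95.7% | 95.3% | 89.6% | 87.1% |

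AN count given HiSCR was 92.6–96.0% (q2w) and 90.9–95.6% (q4w), above flare in every run. A between-regimen correlation of 0.3 or 0.7, checked at endpoint correlations 0 and 0.8, moves the tabulated results by at most 0.5 point.

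**Step 4: enlarged trial.** At 541/3 ≈ 180 per arm without dropout, flare given HiSCR is 94.5–97.2% (q2w) and 93.3–96.9% (q4w). Unconditionally it is 91.1–93.7% and 88.9–92.3%.

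**Step 5: size.** 471 × 1.15 = 541.65, whereas 544/471 = 1.155, a 15.5% increase.

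**The case against.** The best defence is that the conditioning sentence also points to 12.5.1, so the AN-count gate is cross-referenced. A planner may have meant the power of each test at its initial alpha, once reached. With independent endpoints and no alpha passing, AN-count power given HiSCR equals the stand-alone figure, and flare power given both earlier rejections is close to 98/92. On that view, a few added words naming AN count as a further condition for flare would be enough.

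This explains where the numbers came from but does not rescue the label. Independence without alpha passing is stand-alone power under another name, and the section referred to contains both the gate and the alpha passing. Under the actual procedure, flare given both HiSCR and AN count is 97.2–99.7% across the runs, so 92% for q4w is not that quantity. Alpha passing raises q4w flare to 88–95%, but it also raises q4w AN count to 91–96%, so 81% and 92% still do not fit together.

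Several points on size do stand. HiSCR, AN change and flare all draw on the same lesion counts, so zero correlation is unlikely, and so is the 7.5-point gap that depends on it. At correlations of 0.5 to 0.8 the q2w gap is about 2 to 5 points, and it is smaller at 180 per arm. Multiplying the stated q4w figures (0.81 × 0.92 = 74.5%) ignores the alpha passing and would overstate the problem. The SAP supplied is the Week 52 plan and leaves confirmatory testing to the Week 16 SAP, so its power text is background. The differing powering sentences and the 544 are minor.

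**Conclusion.** The point holds. That the four figures are incompatible with their stated condition follows from the test order alone and needs no assumption. They are correct as stand-alone powers, and the label is wrong.

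The size does depend on the assumed correlations. At 157 per arm, q2w flare power given HiSCR is about 2 to 7.5 points below the stated 98%, with the lower part of that range more plausible. For q4w the range includes 92%, so no flare overstatement is shown. There the AN-count figure of 81% is the one that does not describe power given HiSCR under the procedure. The trial remains reasonably powered for flare.

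**What to change.** In Protocol 12.8.2 and SAP section 3:

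- Label 92%/81% (AN count) and 98%/92% (flare) as stand-alone powers at 4%/1% two-sided with 157 per arm. Say that they ignore the HiSCR and AN-count gates and the passing of alpha.
- Beside them, give the simulated power of the full procedure and state the correlations assumed. Under those used here, flare given HiSCR at 157 per arm is about 91–96% (q2w) and 88–95% (q4w).
- Use the same powering sentence in Protocol 12.8 and SAP section 3, and tie it to these figures.
- In SAP section 3, replace 544 with approximately 541.

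The cost is text and one simulation, with no extra patients. The only drawback is a slightly less favourable q2w flare figure.

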13.1 Regulatory and ethical compliance

This clinical study was designed and shall be implemented, executed and reported in accordance with the ICH Harmonized Tripartite Guidelines for Good Clinical Practice, with applicable local regulations (including European Directive 2001/20/EC, US CFR 21), and with the ethical principles laid down in the Declaration of Helsinki.

13.2 Responsibilities of the investigator and IRB/IEC

Before initiating a trial, the investigator/institution must obtain approval/favorable opinion from the Institutional Review Board/Independent Ethics Committee (IRB/IEC) for the trial protocol, written informed consent form, consent form updates, subject recruitment procedures (e.g., advertisements) and any other written information to be provided to subjects. Prior to study start, the investigator is required to sign a protocol signature page confirming his/her agreement to conduct the study in accordance with these documents and all of the instructions and procedures found in this protocol and to give access to all relevant data and records to Novartis monitors, auditors, Novartis/Quality Assurance representatives, designated agents of Novartis, IRBs/IECs, and regulatory authorities as required. If an inspection of the clinical site is requested by a regulatory authority, the investigator must inform Novartis immediately that this request has been made.

13.3 Publication of study protocol and results

The protocol will be registered in a publicly accessible database such as clinicaltrials.gov and as required in EudraCT. In addition, after study completion (defined as last patient last visit) and finalization of the study report the results of this trial will be submitted for publication and posted in a publicly accessible database of clinical trial results, such as the Novartis clinical trial results website and all required Health Authority websites (e.g. Clinicaltrials.gov, EudraCT etc.) .

For details on the Novartis publication policy including authorship criteria, please refer to the Novartis publication policy training materials that were provided at the trial investigator meetings.

13.4 Quality Control and Quality Assurance

Novartis maintains a robust Quality Management System (QMS) that includes all activities involved in quality assurance and quality control, to ensure compliance with written Standard Operating Procedures as well as applicable global/local GCP regulations and ICH Guidelines.

Audits of investigator sites, vendors, and Novartis systems are performed by auditors, independent from those involved in conducting, monitoring or performing quality control of the clinical trial. The clinical audit process uses a knowledge/risk based approach.

Audits are conducted to assess GCP compliance with global and local regulatory requirements, protocols and internal SOPs, and are performed according to written Novartis processes

14 Protocol adherence

This protocol defines the study objectives, the study procedures and the data to be collected on study participants. Additional assessments required to ensure safety of subjects should be administered as deemed necessary on a case by case basis. Under no circumstances including incidental collection is an investigator allowed to collect additional data or conduct any additional procedures for any purpose involving any investigational drugs under the protocol, other than the purpose of the study. If despite this interdiction prohibition, data, information, observation would be incidentally collected, the investigator shall immediately disclose it to Novartis and not use it for any purpose other than the study, except for the appropriate monitoring on study participants.

Investigators ascertain they will apply due diligence to avoid protocol deviations. If an investigator feels a protocol deviation would improve the conduct of the study this must be considered a protocol amendment, and unless such an amendment is agreed upon by Novartis and approved by the IRB/IEC and Health Authorities, where required, it cannot be implemented.

16.1 Appendix 1: Clinically notable laboratory values and vital signs

The following criteria will be used to define expanded limits and notable abnormalities of key laboratory tests.

No specific action is pre-defined within this protocol to respond to specific abnormal laboratory values, as it will be decided by the investigator whether and which specific action needs to be taken to respond to any abnormal values, taking into account the overall status of the subject.

Liver Function and Related Variables

Alanine transaminase (ALT) (SGPT): $> 3 \times$ Upper Limit of Normal (ULN)

Aspartate transaminase (AST) (SGOT): $> 3 \times$ ULN

Total bilirubin: $> 2 \times$ ULN

Alkaline phosphatase (ALP): $> 2.5 \times$ ULN

Renal Function

Creatinine (serum): $> 1.5 \times$ ULN

Hematology

Hemoglobin: ≥ 2 g/dl decrease from baseline

Platelet count: $<$ Lower Limit of Normal (LLN)

White blood cell count: $< 0.8 \times$ LLN

Neutrophils: $< 0.9 \times$ LLN

Eosinophils: $> 1.1 \times$ ULN

Lymphocytes: $> 1.1 \times$ ULN

Urinalysis

Protein urine dipstick: ++*

* ++ is ≥ 100 mg/dl

[figure not shown]
16.2 Appendix 2: Blood samples collection

Table 16-1 Blood log: Time schedule for blood sampling

Period	Visit Name	Hematology	Clinical Chemistry	Serum pregnancy test	Blood sample for PK		Blood sample for IG		Biomarker	TB test	Total volume (ml)
		Volume (ml)	Volume (ml)	Volume (ml)	Dose Ref. ID#	Volume (ml)	Volume (ml)	Volume (ml)	Volume (ml)	Volume (ml)	
Screening	Screening 1	4.8	3.5	2						4	14.3
	Screening 2										0
Treatment Period 1	Baseline	4.8	5		1	2	2	15			28.8*
	Week 1										0
	Week 2	4.8	3.5								8.3
	Week 3										0
	Week 4	4.8	3.5								8.3
	Week 8	4.8	3.5								8.3
	Week 12	4.8	3.5								8.3
	Week 16/EOT1	4.8	5		2	2	2	15			28.8
Treatment Period 2	Week 17										0
	Week 18	4.8	3.5								8.3
	Week 19										0
	Week 20	4.8	3.5								8.3
	Week 24				3	2					2
	Week 28	4.8	3.5								8.3
	Week 32										0
	Week 36										0
	Week 40										0
	Week 44	4.8	3.5								8.3
	Week 48										0
	Week 52/EOT2	4.8	5		4	2	2	15	4		32.8

Period	Visit Name	Hematology	Clinical Chemistry	Serum pregnancy test	Blood sample for PK		Blood sample for IG	Biomarker	TB test	Total volume (ml)
		Volume (ml)	Volume (ml)	Volume (ml)	Dose Ref. ID [#]	Volume (ml)	Volume (ml)	Volume (ml)	Volume (ml)	
Post-Treatment Follow-Up	Week 60	4.8	3.5		4	2	2			12.3

* For patients who sign optional DNA sampling ICF, 3 ml of blood will be additionally collected at baseline visit. # Dose reference IDs 1, 2 and 3 are collected pre-dose; scheduled post-dose time points for dose reference ID 4 are collected 2 and 10 weeks post-last study dose.

16.3 Appendix 3: Type I alpha for the pain hypothesis

Pain will be analyzed based on pooled data. Detailed information are listed in below table:

Table 16-2 Type I alpha for the pain hypothesis

Scenario	Hypothesis rejected within two studies							Alpha for pooled pain
	300q2 w HiSCR	300q2w AN count	300q2 w Flare	300q4w HiSCR	300q4w AN count	300q4w Flare	300q2w Pooled Pain	300q4w Pooled Pain
	H_1, H'_1	H_3, H'_3	H_5, H'_5	H_2, H'_2	H_4, H'_4	H_6, H'_6	H_7	H_8
1	Y	N	N	N	N	N	$4\alpha/5-\alpha^2$	-
2	Y	Y	N	N	N	N	$4\alpha/5-\alpha^2$	-
3	Y	Y	Y	N	N	N	$4\alpha/5-\alpha^2$	-
4	N	N	N	Y	N	N	-	$\alpha/5-\alpha^2$
5	N	N	N	Y	Y	N	-	$\alpha/5-\alpha^2$
6	N	N	N	Y	Y	Y	-	$\alpha/5-\alpha^2$
7	Y	N	N	Y	N	N	$4\alpha/5-\alpha^2$	$\alpha/5-\alpha^2$
8	Y	Y	N	Y	N	N	$4\alpha/5-\alpha^2$	$\alpha/5-\alpha^2$
9	Y	Y	Y	Y	N	N	$4\alpha/5-\alpha^2$	$\alpha/5-\alpha^2$
10	Y	N	N	Y	Y	N	$4\alpha/5-\alpha^2$	$\alpha/5-\alpha^2$
11	Y	Y	N	Y	Y	N	$4\alpha/5-\alpha^2$	$\alpha/5-\alpha^2$
12	Y	Y	Y	Y	Y	N	$4\alpha/5-\alpha^2$	$\alpha/5-\alpha^2$
13	Y	N	N	Y	Y	Y	$4\alpha/5-\alpha^2$	$\alpha/5-\alpha^2$
14	Y	Y	N	Y	Y	Y	$4\alpha/5-\alpha^2$	$\alpha/5-\alpha^2$
15	Y	Y	Y	Y	Y	Y	$4\alpha/5$	$\alpha/5$

For scenario 1, 2 and 3, where H_1, H'_1 are rejected, and H_2, H'_2 are not rejected, then H_7 could be tested at level $4\alpha/5-\alpha^2$, and H_8 cannot be tested.

For scenario 4, 5 and 6, where H_2, H'_2 are rejected, and H_1, H'_1 are not rejected, then H_8 could be tested at level $\alpha/5-\alpha^2$, and H_7 cannot be tested.

For scenario 7 to 14, where H_1, H'_1, H_2, H'_2 are rejected, and at least one of the hypothesis $H_3, H'_3, H_4, H'_4, H_5, H'_5, H_6, H'_6$ are not rejected, then H_7 and H_8 could be tested. Initially, H_7 is tested at level $4\alpha/5-\alpha^2$ and H_8 is tested at level $\alpha/5-\alpha^2$. If H_7 (H_8) is rejected, H_8 (H_7) can be tested at level $\alpha-2\alpha^2$.

For scenario 15 where $H_1, H'_1, H_2, H'_2, H_3, H'_3, H_4, H'_4, H_5, H'_5, H_6, H'_6$ are all rejected, then H_7 and H_8 could be tested at level α . Initially, H_7 is tested at level $4\alpha/5$ and H_8 is tested at level $\alpha/5$. If H_7 (H_8) is rejected, H_8 (H_7) can be tested at level α .

The subtraction of α^2 would be subtracted in the initial significance level for pain hypothesis (H_7 and/or H_8) is to account for the maximum possible type I error to claim a success for HiSCR, AN count and/or Flare in both studies. Therefore, the type I error rate is controlled at level α for the submission on all hypothesis endpoints. Under the global null hypothesis (i.e. no difference between secukinumab and placebo), the testing procedure outlined above controls

the type I error rate (one-sided) at the study-level to <0.025 , and at the submission level to $<0.000625 (=0.025^2)$. Considering all possible configurations of true and false null hypotheses, the type I error control at the level of the submission is <0.000625 for the primary objectives, and <0.025 for all hypotheses ([Bretz et al 2019](#)).

**Document History – Changes compared to previous final version of SAP**

Date	Time point	Reason for update	Outcome for update	Section and title impacted (Current)

## List of abbreviations

AE	Adverse event
ALP	Alkaline Phosphatase
ALT	Alanine aminotransferase
AN	Abscesses and inflammatory nodules
AST	Aspartate aminotransferase
ATC	Anatomical Therapeutic Classification
COVID-19	Coronavirus disease of 2019
CM	Concomitant Medication
CRF	Case Report Form
CSR	Clinical Study report
CTCAE	Common Terminology Criteria for Adverse Events
DLQI	Dermatology Life Quality Index
DMC	Data Monitoring Committee
EOT	End of Treatment
EQ-5D	EuroQol-5 Dimension
FAS	Full Analysis Set
GGT	Gamma-Glutamyl Transferase
HLT	High Level Term
HS	Hidradenitis suppurativa
HS-PGA	Hidradenitis Suppurativa Physician's Global Assessment
ICE	Intercurrent event
MedDRA	Medical Dictionary for Drug Regulatory Affairs
MAR	Missing at random
MELRM	Mixed Effect Logistic Regression Model
mHSS	modified Hidradenitis Suppurativa Score
MMRM	Mixed Model for Repeated Measures
NRS	Numerical Rating Scale
PD	Pharmacodynamic(s)
PFS	Pre-filled syringe
PGI-c	Patient Global Impression of change
PGI-s	Patient Global Impression of severity
PK	Pharmacokinetics
PRO	Patient-reported Outcomes
QoL	Quality of Life
Q2W	Once every two weeks
Q4W	Once every four weeks
RAP	Report and Analysis Process
RDO	Retrieved drop-out
RMP	Risk management plan
SAP	Statistical Analysis Plan
SCC	Skin squamous cell carcinoma
S.C.	Subcutaneous

SAE                    Serious adverse event  
SOC                    System Organ Class  
TS                    Trial statistician  
TFL                   Tables, Figures, Listings  
WHO                   World Health Organization

